2. OBJECTIVES

Primary Objective: To investigate if multimodal prehabilitation could decrease postoperative complications and improve functional capacity pre- and postoperatively for patients undergoing colorectal surgery for cancer.

Secondary Objective(s): To investigate the effects of multimodal prehabilitation on Health Related Quality of Life, nutritional status, length of hospital stay and cost-effectiveness.

3. STUDY DESIGN

This is an international multicenter, randomized controlled trial with two randomized groups. Patients of adult (>18 years) age undergoing elective colorectal resection for cancer are eligible for inclusion. A total of 708 patients will be included in six participating centers (Copenhagen, Veldhoven, Montréal, Barcelona, Ferrara, Paris). Study will aim to start may of 2017 in Máxima Medical Center, Veldhoven, The Netherlands, and in Montréal General Hospital, Canada, and in 2017 in the other participating centers. Inclusion of patients will take approximately 2 years and the follow-up is 1 year.

The control group in this study will receive standard care according to international ERAS protocol.

An overview of the measurements during the PREHAB study can be found in appendix I. These measurements will be applied in the control group as well as the intervention group.

4. STUDY POPULATION

4.1 Population (base)

Colorectal cancer patients in Máxima Medical Center, scheduled for elective surgery.

4.2 Inclusion criteria

In order to be eligible to participate in this study, a subject must meet all of the following criteria:

Adult patients (>18 years) undergoing elective colorectal surgery for cancer.

4.3 Exclusion criteria

A potential subject who meets any of the following criteria will be excluded from participation in this study:

- metastatic disease known preoperatively,
- paralytic or immobilized patients (not capable to perform exercise or 6MWT),
- premorbid conditions or orthopedic impairments that contraindicated exercise,
- cognitive disabilities,
- chronic renal failure (dialysis or creatin > 250 mmol)
- ASA score 4 or higher,
- illiteracy,
- abdominoperineal resection (inability to perform postoperative tests).

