5. TREATMENT OF SUBJECTS

5.1 Investigational product/treatment

1. Patient triage medical conditions

Patient triage will allow us to tailor perioperative management, which may lower the risk for postoperative complications 30% in 'the risky' group. An anaerobic threshold (AT) value of the VO₂max test of 10 ml/kg/min gives 0.88 specificity and 0.79 sensitivity with area under curve of 0,85 for risk of complications.⁵³ Also severe pulmonary and cardiac disease will often be detected and scaled upon severity with exercise testing.

Triage will also focus on anemia, to identify patients' cardiopulmonary comorbidity using VO₂ peak tests. Patients will be screened preoperatively (4 weeks before surgery) to capture insufficient hemoglobin levels (thresholds in Canada: >11.2 g/dl, Europe: >7mmol/l). In case of iron insufficiency, hemoglobin levels will be optimized using iron injections. In combination with training it may give substantial effect.

Triage described above will be applied to the intervention group as well as controls.

2. Prehabilitation intervention

The intervention described below will only be given to the intervention arm of this study. The only exception is the smoke-cessation program, which will be offered to all patients.

Exercise program

An exercise specialist (kinesiologist, sport physician) will assess patients' mobility and capacity to undertake exercise. All participants will undergo a cardiopulmonary exercise test (CPET) and the exercise intensity will be defined and personalized on the individual CPET values. Based on the evaluation, a personalized program from the standardized program will be coordinated, as defined in appendix II. Additional to the preoperative exercise program, patients will receive information regarding breathing techniques to prevent occurrence of pneumonia.

With the intervention we try to achieve a maximum training stimulus in combination with a recovery diet, in order to achieve these goals in 4 weeks.

The program exists of several components:

- Strength training and high intensity interval training: this will be done 3 times a week supervised in the hospital. The strength training consists of 2 series of 10 repetitions of 6 exercises targeting all major muscle groups. The high intensity interval training aimed at 90% of the VO₂-peak
- Homework endurance training (low to moderate intensity): 4 times a week done at home.

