Since vitamin D is associated with muscle mass and muscle strength,^{63, 64} vitamin D will be supplemented daily according to guidelines of the Health Council of the Netherlands (10 µg for women aged 50-69y, for men <70y and women <50y with colored skin and/or little sun exposure and 20 µg for women and men aged 70 y or older).⁶⁵ Besides vitamin D, many elderly patients may have other micronutrient deficiencies or ingest vitamins and minerals below recommended doses before and after surgery. Therefore, all other vitamins and minerals are supplied in a multivitamin/mineral supplement containing 50% of the recommended daily allowance.

During the period of hospitalization, the time (in days) that patients consume nil per mouth is recorded. Also, on the day of discharge, a trained dietician performs a 24-hour recall questionnaire to estimate oral protein- and energy intake.

Nutritional status assessment (PG-SGA and weight gain or loss) will be performed at 4 and 8 weeks post-surgery by an investigator – trained by a registered dietician.

Protein supplementation

Resistance training and protein supplementation have synergistic effects on muscle protein synthesis.^{25,43,66,67} In young healthy men, consumption of as little as 20-25 g of protein immediately following physical activity has shown to improve muscle accretion.^{68,69,70} Due to anabolic resistance, elderly subjects require higher amounts of protein to obtain exercise-induced anabolism. Studies show that ingestion of 30-40 g of high quality dietary protein immediately after a bout of exercise may best support reconditioning in older adults.⁷¹ Furthermore, the amount and amino acid composition of the post-exercise protein source is of particular importance. An amount of 6-10 g of essential amino acids (EAA) has shown to optimally stimulate muscle protein synthesis in healthy young men.⁷² Of all EAA, especially leucine appears to be a strong stimulus for protein synthesis. It is suggested that the post-exercise protein source should contain 2-3 g of leucine in both young and older adults.^{73, 74} The exercise-induced enhanced sensitivity to the anabolic properties of amino acids in muscle mass is retained for at least 24 hours following physical activity. Studies have shown that ingestion of protein before sleep may prolong muscle protein synthesis during overnight post exercise recovery.⁷⁵

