- *Lobar atelectasis*: radiological finding of at least one lobar collapse.⁴
- *Pleural fluid*: pleural effusion requiring drainage of the pleural cavity.
- *Respiratory failure*: delayed extubation > 24 hours after primary surgery, or reintubation at any time for ventilatory support.⁴
- *Pulmonary edema*: clinical signs and radiological confirmation.⁷

Other medical

- *Acute Kidney Injury*: increase in serum creatinine $\times 2$ from baseline or reduction of glomerular filtration rate greater than 50%.⁸
- *Urinary retention*: Reinsertion of indwelling urinary catheter after removal attempt or patient discharged with urinary drainage (excluding patients with permanent indwelling urinary catheter).
- *Anemia*: low serum hemoglobin requiring transfusion of PRBC, unrelated to any identified source of bleeding.
- *Hepatic dysfunction*: Increased serum bilirubin concentration $> 34 \mu\text{mol/l}$ (2 mg/dl) compared to preoperative value AND elevated liver enzymes AND has NOT undergone a pancreaticobiliary procedure.⁴
- *Acute Pancreatitis*: diagnosis requires 2 of the following: upper abdominal pain of acute onset often radiating through to the back; increase in serum amylase or lipase ($\times 3$ normal value); cross-sectional abdominal imaging consistent with acute pancreatitis.⁹
- *Other gastrointestinal complications*: any other complication of the gastrointestinal tract requiring treatment (e.g. blood per rectum, diarrhea, high stoma output).
- *Neurological complications*: any neurological complication excluding cerebrovascular events or anesthesia-related injuries (e.g. epileptic seizure)

- *Psychiatric complications*: new psychiatric symptoms including delirium and depression, requiring pharmacological treatment.

INFECTIOUS

- *UTI*: upper or lower urinary symptoms and urine culture with no more than two species of organisms, at least one of which is a bacteria of $\geq 10^5$ CFU/ml.¹⁰
- *Wound infection*: Purulent drainage, with or without positive culture, from the superficial incision or any sign or symptom of infection (e.g. pain or tenderness, localized swelling, redness) and superficial incision is deliberately opened by the surgeon or attending physician. Not included if part of intra-peritoneal abscess.¹¹
- *Intra- or retroperitoneal abscess*: Radiologic finding of deep collection of pus associated with systemic signs of infection or finding during reoperation.

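### The renal exclusion prints its creatinine limit in millimoles with no volume, a factor of 1000 too high, so read literally only dialysis can exclude a patient under it

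*Protocol*

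**What the plan says.** The list in section 4.3 of the Protocol is disjunctive: "A potential subject who meets any of the following criteria will be excluded from participation in this study". One of its entries is "chronic renal failure (dialysis or creatin > 250 mmol". That entry has two limbs, dialysis and a creatinine limit. The limit is given in millimoles with no volume, and the analyte appears as *creatin*.

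The only other creatinine rule is the definition of acute kidney injury in Appendix IV, which starts "increase in serum creatinine", requires a doubling, and continues "from baseline or reduction of glomerular filtration rate greater than 50" per cent. It is relative to the patient's own baseline and gives no absolute level.

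Other laboratory limits in the Protocol carry a volume. Section 5.1 gives haemoglobin as "thresholds in Canada: >11.2 g/dl, Europe: >7mmol/l". The hepatic dysfunction entry in Appendix IV gives bilirubin as 34 micromol/l with its conventional equivalent, "2 mg/dl) compared to preoperative value AND elevated liver enzymes".

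**The concern.** Serum creatinine at the level of chronic renal failure is measured in hundreds of micromoles per litre. A limit of 250 in millimoles is not a level that any patient could have, so the creatinine limb as printed cannot exclude anyone.

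At stake is whether the eligibility text does what it is meant to do. Six centres (Copenhagen, Veldhoven, Montréal, Barcelona, Ferrara, Paris) work from it, and section 5.1 shows that the sponsor expects different laboratory units in Canada and Europe. A monitor holding a centre to the printed words could not record the enrolment of a non-dialysis patient with, say, 400 micromol/l as a breach of this criterion.

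This is also the only exclusion in section 4.3 that names renal function, and the intervention raises protein intake to 1.5-1.8 g/kg/day. The protein calculation in section 8.3 is adjusted for BMI but not for renal function. That renal impairment matters for such a diet is general clinical judgement and is not stated in the Protocol, but it is a reason to have the cut-off right.

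**Working it through.** **Inputs**

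- Printed limit: 250 mmol, no volume (Protocol, section 4.3).
- Molar mass of creatinine: 113.12 g/mol. This is a physical constant that the Protocol does not give. The factor of 1000 does not depend on it.
- Assumption: the missing volume is one litre, as in the Protocol's other molar limits.

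**Printed limit, read per litre**

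- 250 mmol/l = 0.250 mol/l = 250,000 micromol/l
- 0.250 mol/l × 113.12 g/mol = 28.28 g/l
- 28.28 g/l × 100 = 2828 mg/dl

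**Evident intended limit**

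- 250 micromol/l = 0.000250 mol/l
- 0.000250 mol/l × 113.12 g/mol = 0.02828 g/l
- 0.02828 g/l × 100 = 2.83 mg/dl

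**Ratio:** 0.250 / 0.000250 = 1000.

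**Reading without adding a volume.** 250 mmol is then an amount, 0.250 mol × 113.12 g/mol = 28.28 g, and not a concentration. It cannot be compared with a serum result at all. Neither reading gives a usable limit.

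**What passes the criterion as written.** Per litre, every non-dialysis value above 250 and up to 250,000 micromol/l (2.83 to 2828 mg/dl). The example of 400 micromol/l is 0.000400 × 113.12 × 100 = 4.52 mg/dl. It lies above the evident limit and far below the printed one.

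**Does the Protocol handle such units correctly elsewhere?** Yes. For bilirubin, with a molar mass of 584.66 g/mol (again an outside constant), 34 micromol/l gives 0.000034 × 584.66 × 100 = 1.99 mg/dl, which agrees with the 2 mg/dl in Appendix IV. The fault is confined to the line in section 4.3.

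**Does another place supply the value?** No. Appendix IV defines kidney injury only as a change from baseline, and no other section restates the renal exclusion.

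**The case against.** The strongest reply is that this is a slip that announces itself. The entry opens with the words for chronic renal failure, the printed level is impossible, and a clinician will read it as 250 micromol/l. A wrong but plausible limit would be more dangerous. Other rules limit the consequence: ASA 4 or higher is excluded, so are conditions that contraindicate exercise, and section 5.1 has every participant assessed for exercise and tested by CPET. No analysis depends on the number. All of this stands, and it is why the practical effect is judged small. It does not make the text right, and none of those rules is a creatinine limit.

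A second reply is that the literal reading is selective: it supplies the litre and the analyte but refuses to correct the prefix. That is fair as a comment on how the line would be used. It does not rescue the limit, because the reading without a volume cannot be applied either.

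A third is that a micro sign misread when the PDF was converted to text would give exactly this prefix. This cannot be ruled out. The sign survives in section 5.1 ("10 µg for women aged 50-69y") and in the bilirubin limit in Appendix IV, which makes it unlikely but does not prove it for this line. Such a misreading would not account for the missing volume or the misspelt analyte, so the line would need correction even then.

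**Conclusion.** The concern holds. The creatinine limit in section 4.3 is wrong as written by a factor of 1000 and lacks a volume. Read literally, only dialysis can trigger the renal exclusion. This is an operative eligibility threshold, so it should be corrected and not left for each centre to infer.

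The conclusion rests on three things: that the limit was meant per litre; that micromoles were intended, which is inferred from physiology because the Protocol never states it; and that the prefix is not an artefact of text conversion. The number of patients affected cannot be given, because the Protocol reports no creatinine distribution; it is probably very small. The primary endpoints, the sample size of 708 and the error rates are unaffected.

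**What to change.** Reword the entry in section 4.3 as: chronic renal failure (dialysis or serum creatinine > 250 micromol/l, about 2.8 mg/dl). The sponsor should confirm that 250 micromol/l is the value meant. Giving both units follows what Appendix IV does for bilirubin and serves centres that report in either.

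The cost is one line in an amendment. Design, sample size and analysis do not change.

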4.4 Sample size calculation

The sample size calculation is based on the primary aim, to lower postoperative complications as determined according to the CCI score. With our population variables, CCI mean is 10.4 (SD 14), aiming to see decrease of 30%. We use an alpha of 0.05 and power of 0.80 (two-sided test). 10% dropouts are expected. We than need 708 patients, 354 per arm. This gives us a 100% efficacy to see a 6MWT proportion of improvement difference (55% versus 20%) as observed in previous studies.^{7,8} Each year around 800 eligible CRC patients undergo surgery in the participating hospitals in total, indicating that we will finish inclusion within 2 year time, with subsequent follow-up of 1 year.

5. TREATMENT OF SUBJECTS

5.1 Investigational product/treatment

1. Patient triage medical conditions

Patient triage will allow us to tailor perioperative management, which may lower the risk for postoperative complications 30% in 'the risky' group. An anaerobic threshold (AT) value of the VO₂max test of 10 ml/kg/min gives 0.88 specificity and 0.79 sensitivity with area under curve of 0,85 for risk of complications.⁵³ Also severe pulmonary and cardiac disease will often be detected and scaled upon severity with exercise testing.

Triage will also focus on anemia, to identify patients' cardiopulmonary comorbidity using VO₂ peak tests. Patients will be screened preoperatively (4 weeks before surgery) to capture insufficient hemoglobin levels (thresholds in Canada: >11.2 g/dl, Europe: >7mmol/l). In case of iron insufficiency, hemoglobin levels will be optimized using iron injections. In combination with training it may give substantial effect.

Triage described above will be applied to the intervention group as well as controls.

2. Prehabilitation intervention

The intervention described below will only be given to the intervention arm of this study. The only exception is the smoke-cessation program, which will be offered to all patients.

Exercise program

An exercise specialist (kinesiologist, sport physician) will assess patients' mobility and capacity to undertake exercise. All participants will undergo a cardiopulmonary exercise test (CPET) and the exercise intensity will be defined and personalized on the individual CPET values. Based on the evaluation, a personalized program from the standardized program will be coordinated, as defined in appendix II. Additional to the preoperative exercise program, patients will receive information regarding breathing techniques to prevent occurrence of pneumonia.

With the intervention we try to achieve a maximum training stimulus in combination with a recovery diet, in order to achieve these goals in 4 weeks.

The program exists of several components:

- Strength training and high intensity interval training: this will be done 3 times a week supervised in the hospital. The strength training consists of 2 series of 10 repetitions of 6 exercises targeting all major muscle groups. The high intensity interval training aimed at 90% of the VO₂-peak
- Homework endurance training (low to moderate intensity): 4 times a week done at home.
- Diet and rest: the diet is focused on a protein intake of 1,5-1,8 g/kg/day with 0,4 g/kg/day whey proteins after training and 0,4 g/kg/day casein proteins before bedtime. This is further explained in the nutrition section of the protocol.

With the training program we try to achieve the following improvements:

- Increase of 10% of VO₂-peak
- Increase of 15% of VO₂-peak at AT
- Increase of 20-40% in 1RM tests (or increase in dumbbell weight)
- Increase in the distance of 10% at 6MWT (at <500m)
- Decrease of 10% of the stairs climb test

At baseline, after prehabilitation (1 week before surgery) and 4 weeks after surgery CPET will be performed. At baseline, the week before surgery, 4 and 8 weeks postoperatively, muscle strength will be tested with the sit-to-stand test, 1-RM and handgrip strength. Functional capacity will be tested at the same time points using the 6-minute walk test and stair climb test. Patients in both groups will wear an accelerometer during four weeks before surgery and four weeks after surgery in order to estimate (changes) in physical activity outside of the hospital in the control and intervention group.

Determine AT:

While slowly increasing the resistance, the VO₂, VCO₂ and VE (expired ventilation) will initially rise linear, up to the moment lactic acidosis develops. With effort above the anaerobic threshold (AT) the CO₂ rises faster than the O₂ uptake, because the CO₂ produced from HCO₃⁻, by buffering lactate, is added to the CO₂ production. VE rises with the increase of CO₂ output (isocapnic buffering), there is still a linear relation whereby EQCO₂ (VE/VCO₂) remains constant (or a light decrease), while EQO₂ (VE/VO₂) increases.

- Increase of VE/VO₂, while VE/VCO₂ remains constant (or light decreases).
- Increase of PETO₂ (change in linearity) vs workload.
- V-slope: change in linearity of VO₂ vs VCO₂

Determine RCP:

If the workload (Watt) after AT further increases, VE rises faster than de CO₂ output, i.e. a rise of EQCO₂ (VE/VCO₂), which ensures for a decrease of PaCO₂ and PETCO₂ (hyperventilation). The point at which the VE rises more than needed for the CO₂, and the PETCO₂ decreases is a 'extra' ventilatory response and is also called 'respiratory compensation point' (RCP). The increase of H⁺ concentration stimulates the carotic bodies (vascular glands) to increase the ventilatory drive as a reaction at the lactic acidosis. By an increase of VE the arterial PCO₂ decreases.

- Increase of VE/VCO₂ vs workload
- Decrease of PETCO₂ vs workload.
- VE vs VCO₂: change in linearity

Nutritional supplements

To enhance the anabolic effect of physical training, improve lean body mass and obtain or maintain an optimal nutritional status during the prehabilitation period, sufficient intake of nutrients (especially energy and protein) is required. The schedule for the nutritional intervention can be found in Appendix III.

A registered dietician will assess patients' nutritional status at baseline and at the end of the exercise program, using the Patient Generated Subjective Global Assessment (PG-SGA). Furthermore, a set of anthropometric measurements (including body weight, length, triceps skinfold, hand grip strength and circumferences of wrist, waist and upper arm) is performed to allow assessment of (change in) body weight, (subcutaneous) fat mass, (upper limb) muscle mass and muscle strength, taking into account patients' body frame.

The patient will fill in a three-day food diary (including two week days and one weekend day), which will provide an estimate of habitual macronutrient consumption⁵⁴ as analyzed using a commercially available software program.⁵⁵ Based on estimated habitual protein intake, participants will receive a tailored dietary advice aiming a total protein intake of 1,5 (- max 1,8) gram / kg daily.^{56,57} Also, patients will be recommended to evenly 'spread' their protein intake over 3 meals with a minimum of 25-30 gram of protein/ meal.⁵⁸ To stimulate muscle protein synthesis, participants will also be provided with a protein (0,4 gram/kg/day) supplement immediately after strength training (3 times a week) and daily before sleep.

Patients' energy requirements will be estimated according to the revised Harris and Benedict equation⁵⁹ using stress- and activity factors between 1,3 and 1,5. Recommendations to change energy intake will not only be based on discrepancies between estimated energy intake and energy requirements, but also on (changes in) nutritional status parameters, such as weight loss. This is done because underreporting of true energy intake is commonly seen with self-reported dietary assessment^{60, 61} and can increase up to 50% in overweight people.⁶²

Since vitamin D is associated with muscle mass and muscle strength,^{63, 64} vitamin D will be supplemented daily according to guidelines of the Health Council of the Netherlands (10 µg for women aged 50-69y, for men <70y and women <50y with colored skin and/or little sun exposure and 20 µg for women and men aged 70 y or older).⁶⁵ Besides vitamin D, many elderly patients may have other micronutrient deficiencies or ingest vitamins and minerals below recommended doses before and after surgery. Therefore, all other vitamins and minerals are supplied in a multivitamin/mineral supplement containing 50% of the recommended daily allowance.

During the period of hospitalization, the time (in days) that patients consume nil per mouth is recorded. Also, on the day of discharge, a trained dietician performs a 24-hour recall questionnaire to estimate oral protein- and energy intake.

Nutritional status assessment (PG-SGA and weight gain or loss) will be performed at 4 and 8 weeks post-surgery by an investigator – trained by a registered dietician.

Protein supplementation

Resistance training and protein supplementation have synergistic effects on muscle protein synthesis.^{25,43,66,67} In young healthy men, consumption of as little as 20-25 g of protein immediately following physical activity has shown to improve muscle accretion.^{68,69,70} Due to anabolic resistance, elderly subjects require higher amounts of protein to obtain exercise-induced anabolism. Studies show that ingestion of 30-40 g of high quality dietary protein immediately after a bout of exercise may best support reconditioning in older adults.⁷¹ Furthermore, the amount and amino acid composition of the post-exercise protein source is of particular importance. An amount of 6-10 g of essential amino acids (EAA) has shown to optimally stimulate muscle protein synthesis in healthy young men.⁷² Of all EAA, especially leucine appears to be a strong stimulus for protein synthesis. It is suggested that the post-exercise protein source should contain 2-3 g of leucine in both young and older adults.^{73, 74} The exercise-induced enhanced sensitivity to the anabolic properties of amino acids in muscle mass is retained for at least 24 hours following physical activity. Studies have shown that ingestion of protein before sleep may prolong muscle protein synthesis during overnight post exercise recovery.⁷⁵

Therefore, participants of PREHAB Intervention group will receive protein supplementation immediately following exercise and (± 30 minutes) before sleep, providing a standard dosage of 25 g of a high quality protein source that contains at least 10 g of EAA, of which 2-3 g leucine.

Smoke cessation

Cigarette smoking itself is a well-known risk factor for postoperative complications. Smoking has a transient effect on the tissue microenvironment and a prolonged effect on inflammatory and reparative cell functions leading to delayed healing and complications.⁷⁶ A period of 4 to 8 weeks

smoking cessation prior to surgery has already been shown to significantly reduce postoperative complications and morbidity.⁷⁷ A smoke cessation program including intensive counseling and nicotine replacement therapy (NRT) will be offered to all patients – including patients in the control group – during the 4 weeks prior to the surgery. Approximately 15-20% of our patients are current smokers at the moment of cancer diagnosis. The goal is to achieve a smoke cessation percentage of 80 before surgery.

Psychological coping

It is expected that patients undergoing surgery for cancer are anxious with some component of depression. Since both anxiety and depression can influence the motivation to carry out social and functional activities, psychological strategies can be put in place to help patients to cope with the stress of surgery and disease. Therefore, patients will be screened for anxiety and depression using the GAD-7 and PHQ-9 questionnaires. If these questionnaires result in a high score (GAD-7 of 10 or higher; PHQ-9 score 15 or higher), patients are considered high-risk and will be offered a referral to a psychologist. Referred patients will receive a total of 1.5 hours of psychological intervention in the first session and more sessions during the 4 weeks of prehabilitation if necessary. In this preoperative session, the first hour will address the patient's anxieties, coping strategies, and post-operative expectations, with the goal of optimizing psychological well-being & ways of coping with surgery. The importance of the patient's active participation in the healing process will also be discussed.

All patients in the intervention group will be given instructions on relaxation and breathing techniques by a trained investigator. They will be given an instruction CD, which they can use for relaxation techniques at home. After the program, patients will be asked if their perceived usefulness of these techniques.

Also, as a form of psychological support, the intervention group will be contacted weekly by the investigator by phone. During these 5-15 minute phone calls, a researcher will shortly evaluate the following themes:

- General health perception of the patient: "how are you doing?"
- Evaluation of anxiety and use of anxiety reduction techniques.
- Evaluation of training: attendance, side effects/injuries, factors limiting attendance or completion of exercises.
- Evaluation of dietary intervention (protein supplement and advice): evaluate adherence and side effects.
- If relevant: smoking-cessation. Perception of usefulness of the program, smoking status (active smoker/stopped?), side effects.
- Any other questions the patient may have.

In order to enhance adherence to the prehabilitation program, all patients in the intervention group will receive an instructional brochure that includes information about all elements of the program.

